6.6 Consent for continuing data review of medical records

During the consent process, patients will have the option to provide permission for future data review of their medical records. This permission allows for study staff to contact the patient (or the patient's caregiver(s)) to obtain medical records and other information for a period of up to two years after the patient has withdrawn from or completed the study. The purpose of this data review is to capture information including but not limited to clinical, radiographic, pathologic, laboratory and pulmonary function data, after the patient has exited the study. The rationale for future data review is that there may be long term effects of COVID-19 or the study drug, that are unknown to the investigators at this time.

7. Stopping rules

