7.1 Participant withdrawal criteria

Participants may be terminated early from the study for the following reasons:

- a. The participant elects to withdraw consent from study activities.
- b. The participant dies.
- c. The participant has a serious allergic or anaphylactic reaction to the study drug
- d. The participant's condition deteriorates significantly necessitating either a transfer to the intensive care unit (ICU) or the need for advanced respiratory support (high flow oxygen ≥ 15 L/minute, CPAP, non-invasive or invasive mechanical ventilation), and the treating clinician thinks it is in the best interest of the patient to be withdrawn \pm unblinded. If the patient is unblinded, any open label use of sirolimus after that will be based on clinical grounds at the discretion of the treating clinician(s). The study drug (sirolimus or placebo) will continue for the maximum stipulated duration of 14 days regardless of escalation in care, unless the patient is withdrawn from the study.
- e. In the opinion of the investigator, it is not in the participant's best medical interest to continue to participate in the study.

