13.1.2 Subject discontinuation

An intent-to-treat approach will be used. All data acquired prior to termination for the reasons outlined below will be included in the primary analysis unless patient withdraws consent. Every effort will be made to conduct a final study visit with the participant and participants will be followed clinically until, if applicable, all AEs attributable to study drug resolve. Please refer to Section 7.1 for a list of the reasons that may lead to participant withdrawal from the study.

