13.1.4 Individual early stopping rules

A study participant will be terminated from the study if any of the following occurs during the study:

- Recurrent or persistent sirolimus-related toxicity unresponsive to treatment in spite of dose adjustments.
- Pregnancy
- The participant refuses to continue in the study
- The investigator determines that the participant should be withdrawn from the study for reasons not listed above

A subject will be considered evaluable if they took one dose of the study drug. Subjects who are withdrawn before initiating treatment will be considered as premature discontinuation, and will be replaced by another participant.

Every effort will be made to obtain endpoint evaluations for subjects who withdraw or who discontinue prematurely from the study. The same evaluations performed at final visit will be completed at the time of termination. If withdrawal is due to inability to tolerate investigational drug or other untoward event related to investigational drug, the withdrawal will be noted in data analysis as treatment failure.

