Data Analysis Plan: The primary endpoint of this study is progression to respiratory failure requiring advanced support measures. The difference in proportions of progression between the placebo and sirolimus groups and the 80% confidence interval will be calculated. If the confidence interval for the difference in proportions does not include zero, then we will conclude that the treatment difference is clinically meaningful. Considering the small sample size of our study, the significant impact of age and other pre-existing conditions such as diabetes mellitus on overall prognosis in patients with COVID-19 cannot be accounted for in the primary analysis. Patients will be randomized according to a computer-generated permuted block randomization stratified on age: <50 years, 50 – 64 years, and ≥ 65 years. In case recruitment lags we will add external study sites. In such a scenario, University of Cincinnati and the facilities of the affiliated health systems UC Health, LLC and University of Cincinnati Physicians Company, LLC will follow the same randomization scheme. In case of other external sites, randomization will be stratified based on site in addition to the above-mentioned age-based stratification. As exploratory analysis, we will conduct analyses examining differences based on other prognostic factors and concomitant medications such as corticosteroids, hydroxychloroquine, azithromycin etc. An intent-to-treat analysis will be performed for the primary outcome.

16. Identification and access to source data

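### Section 13.1.2 leaves data recorded before consent withdrawal out of a primary analysis that is called intent-to-treat, so a primary event already on file can be lost

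*Combined protocol and SAP*

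**What the plan says.** Section 13.1.2 opens with "An intent-to-treat approach will be used" and continues: "All data acquired prior to termination for the reasons outlined below will be included in the primary analysis unless patient withdraws consent". It refers to Section 7.1 for the termination reasons, where reason (a) reads: "The participant elects to withdraw consent from study activities".

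The Data Analysis Plan in protocol Section 15 and in the SAP both state: "An intent-to-treat analysis will be performed for the primary outcome". Neither contains an exception for consent withdrawal or a rule for missing outcomes.

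Three rules in Section 13.1.4 bear on the same patients:

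- On follow-up: "Every effort will be made to obtain endpoint evaluations for subjects who withdraw or who discontinue prematurely from the study".
- On withdrawal because the drug is not tolerated, or because of another drug-related event: "the withdrawal will be noted in data analysis as treatment failure".
- On who counts: "A subject will be considered evaluable if they took one dose of the study drug". Patients withdrawn before starting treatment are replaced, and Section 13.3 limits replacement to non-evaluable participants.

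Section 6.6 adds an optional permission: "During the consent process, patients will have the option to provide permission for future data review of their medical records".

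**The concern.** The sentence in 13.1.2 is about data acquired before termination. Its exception therefore reaches outcomes recorded while consent was in force, which is a separate matter from follow-up lost after a patient leaves. An intent-to-treat analysis keeps patients in the arm to which they were randomised and counts what was observed. A rule that takes out observed outcomes because of something that happened after randomisation does not fit that label.

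The situation can arise. Sections 6.2 and 8.5 record advanced respiratory support every day, and Sections 6.1 and 7.1(d) allow a patient to remain in the trial after progressing. A patient could start non-invasive ventilation on day 4, with the event recorded, and withdraw consent on day 6. Read as written, that event does not enter the primary analysis. If such withdrawals differ between arms, the comparison that decides the trial is biased. With about 10 placebo patients, each exclusion carries weight. A dosed patient who withdraws consent is evaluable and so is not replaced, which means the denominator shrinks as well.

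**Working it through.** **Inputs from Section 15 and the SAP.** N = 30 at 2:1, so 20 sirolimus and 10 placebo; expected proportions 0.50 (placebo) and 0.25 (sirolimus); two-sided type I error 0.2; the treatment difference is declared clinically meaningful if the 80% interval for the difference in proportions excludes zero.

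**Assumptions.** The plan names no interval method, so I use the uncorrected Wald interval with z = 1.2816. The plan gives no consent-withdrawal rate, so the one- and two-patient cases are illustrations.

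**Formula.** d = p_P − p_S; SE = √[p_P(1−p_P)/n_P + p_S(1−p_S)/n_S]; interval d ± 1.2816 × SE.

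**Step 1: the plan's own case, 5/10 against 5/20.** d = 0.50 − 0.25 = 0.250. SE = √(0.0250 + 0.0094) = 0.1854. Half-width = 1.2816 × 0.1854 = 0.2376. Interval 0.012 to 0.488, excluding zero. The sample size of 30 is consistent with its inputs: at N = 27 the same calculation gives -0.0005 to 0.5005. The lower limit at N = 30 clears zero by only 0.012.

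**Step 2: one placebo patient with a recorded event left out, 4/9 against 5/20.** d = 0.4444 − 0.25 = 0.194. SE = √(0.0274 + 0.0094) = 0.1919. Half-width 0.2459. Interval -0.051 to 0.440, including zero.

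**Step 3: other exclusions, same formula.**

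| Starting table | Patient(s) left out | Table analysed | Difference | 80% Wald interval |
|---|---|---|---|---|
| 5/10 v 5/20 | 1 sirolimus, event | 5/10 v 4/19 | 0.289 | 0.054 to 0.525 |
| 5/10 v 5/20 | 1 placebo, no event | 5/9 v 5/20 | 0.306 | 0.060 to 0.551 |
| 5/10 v 5/20 | 1 sirolimus, no event | 5/10 v 5/19 | 0.237 | -0.004 to 0.477 |
| 5/10 v 6/20 | none | 5/10 v 6/20 | 0.200 | -0.042 to 0.442 |
| 5/10 v 6/20 | 2 sirolimus, events | 5/10 v 4/18 | 0.278 | 0.039 to 0.516 |

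An exclusion can remove a positive conclusion or create one.

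**Step 4: dependence on the interval method.**

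- Newcombe: 0.016 to 0.464 for 5/10 v 5/20, and -0.039 to 0.422 for 4/9 v 5/20. The change across zero is the same.
- Agresti-Caffo: 0.006 to 0.449, and -0.046 to 0.410. The same again.
- Continuity-corrected Wald for 5/10 v 5/20: the correction is ½(1/10 + 1/20) = 0.075, giving -0.063 to 0.563. Zero is already included, so there is no positive conclusion to lose. The Fisher p-value for this table is 0.23.

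**Step 5: how typical Step 2 is.** Summing exact binomial probabilities over all tables at rates 0.50 and 0.25, the uncorrected Wald interval excludes zero in about 56% of trials. In about 11% of all trials it excludes zero with full data but includes it once one placebo event is removed.

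**Step 6: bias with no true effect (assumed).** Let the rate be 0.5 in both arms, and let a fraction w of sirolimus patients with events withdraw consent while no placebo patients do. The expected sirolimus proportion becomes 0.5(1−w)/[0.5(1−w) + 0.5]. For w = 0.1, 0.2 and 0.3 this is 0.474, 0.444 and 0.412, a spurious benefit of 0.026, 0.056 and 0.088.

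**The case against.** The exception may have been meant only for patients who refuse further use of their data. Section 13.1.4 lists refusal to continue as a separate reason and promises to seek endpoint evaluations from those who withdraw, which suits that narrower meaning. The consent form is not in the copy reviewed, so what it tells patients about their data cannot be checked. This objection stands as a statement about intent. However, 13.1.2 does not state the limit, 7.1(a) speaks only of study activities, and no other section restores the data.

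The documents also provide other routes out. A patient who deteriorates may be withdrawn by the treating clinician under 7.1(d), which is not consent withdrawal, so those data stay in. Drug-related withdrawal is treated as failure under 13.1.4. Participation is inpatient, lasts at most 14 days and relies largely on chart review, so few patients, perhaps none, may be affected. All of this is fair and limits the likely size. It does not settle which rule applies when a patient withdraws consent because of intolerance: 13.1.4 calls that a treatment failure, while 13.1.2 leaves the data out.

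Finally, this is a 30-patient pilot meant to inform a larger trial, and Step 2 starts from a table that barely clears zero. That is correct, and the intervals should be read as illustrations only.

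**Conclusion.** The point holds. Read plainly, 13.1.2 keeps data acquired before consent withdrawal out of the primary analysis, which contradicts the intent-to-treat statements in the same paragraph, in Section 15 and in the SAP. It is a post-randomisation exclusion that may differ by arm, in a trial small enough for one or two patients to change the declared conclusion.

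A reader might infer three stronger things that the documents do not support:

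- **That one exclusion reverses the result in general.** It does so for the planned table under three interval methods, but not under the continuity-corrected one. Some other single exclusions widen the difference.
- **That consent withdrawal follows deterioration or side effects.** No section gives a rate, cause or arm pattern. Differential withdrawal is a possibility, and its direction is unknown.
- **That records are destroyed.** The text concerns only what enters the primary analysis.

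The defect is therefore a stated rule that can bias the primary comparison in either direction, by an amount the documents do not allow one to estimate.

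**What to change.** In Section 13.1.2, replace the exception with a rule along these lines: *all data collected up to the date of consent withdrawal are kept in the primary analysis, and any primary event recorded by that date is counted; only data whose use the patient expressly refuses are omitted, where that refusal must be honoured.*

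Then:

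1. Repeat the rule in Section 15 and the SAP, which are silent on it.
2. State how a patient who withdraws consent with no recorded event is handled in the primary analysis. Add a best-case/worst-case sensitivity analysis that assigns such patients to event and to no event by arm.
3. Reconcile the rule with Section 13.1.4: say which provision governs a patient who withdraws consent because of intolerance, whether treatment failure counts as a primary event, and how replacing undosed patients fits the intent-to-treat set.
4. Report the number and timing of consent withdrawals by arm, and whether a primary event had been recorded by then.
5. Continue chart review after withdrawal only where the patient permits it. The Section 6.6 permission is optional, and keeping data already collected does not depend on it.

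The cost is a few sentences in the protocol and SAP, a check that the consent form agrees, and one sensitivity table. No extra patients or study procedures are needed.

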13.1.3 Study early stopping rules

Study enrollment will be suspended pending expedited review of all pertinent data by the IRB and the DSMB if any one of the following occurs:

- Death from any cause in any subject judged related to study drug
- Multiple medically similar serious adverse events related to study medication
- Events that, in the opinion of the Principal Investigator contraindicate further dosing of additional subjects

If one of the above-listed stopping rules are met, a prompt cumulative review of safety data and of the circumstances of the event(s) in question will be conducted to determine whether study entry should be resumed, whether the protocol will be modified, or whether the study will be discontinued permanently. Review and approval by the DSMB is required for resumption of the study in the event the study is interrupted because of one of the above-listed events.

13.1.4 Individual early stopping rules

A study participant will be terminated from the study if any of the following occurs during the study:

- Recurrent or persistent sirolimus-related toxicity unresponsive to treatment in spite of dose adjustments.
- Pregnancy
- The participant refuses to continue in the study
- The investigator determines that the participant should be withdrawn from the study for reasons not listed above

A subject will be considered evaluable if they took one dose of the study drug. Subjects who are withdrawn before initiating treatment will be considered as premature discontinuation, and will be replaced by another participant.

Every effort will be made to obtain endpoint evaluations for subjects who withdraw or who discontinue prematurely from the study. The same evaluations performed at final visit will be completed at the time of termination. If withdrawal is due to inability to tolerate investigational drug or other untoward event related to investigational drug, the withdrawal will be noted in data analysis as treatment failure.

13.2 Follow-up after early study termination

Participants who are prematurely withdrawn from study drug exposure due to adverse events will be followed to monitor safety until hospital discharge or until resolution or stabilization of the disqualifying event or until the PI determines that further follow-up is not needed.

13.3 Participant replacement

Participants with early termination from this study will be replaced if they are deemed non-evaluable.

14. Data and Safety Monitoring Plan

The study protocol will be reviewed and approved by the Data and Safety Monitoring Board (DSMB) and the University of Cincinnati IRB prior to study initiation. Participant enrollment may only begin with IRB approved consent forms. This is an interventional exploratory phase II study.

14.1 Study Oversight

The Principal Investigator (PI) has primary oversight responsibility of this clinical trial. The DSMB has oversight responsibility of the Data Safety Monitoring Plan (DSMP) for this clinical trial. The DSMB will review accrual, patterns and frequencies of all adverse events, and protocol compliance on a periodic basis. For this study the DSMB will meet once prior to study activation, and at the following subsequent times: once the study has reached 25% (7 subjects), 50% (15 subjects), 75% (22 subjects) and 100% (30 subjects) of its target enrollment. The DSMB will review the patient safety data at these meetings in an unblinded fashion to assess for participant safety. No interim analysis for efficacy will be performed. The DSMB makes recommendations to the PI regarding the continuation status of the protocol.

The site PI and their research team (co-Investigators, research nurses, clinical trial coordinators, and data managers) are responsible for identifying AEs. Aggregate report - detailed by severity, attribution (expected or unexpected), and relationship to the study drug/study procedures – will be available for site review.

14.2 Adverse Events

This section defines the types of AEs and outlines the procedures for appropriately collecting, grading, recording, and reporting them. Information in this section complies with ICH Guideline E2A: Clinical Safety Data Management: Definitions and Standards for Expedited Reporting and ICH E6: Guideline for Good Clinical Practice, and applies the standards set forth in the National Cancer Institute (NCI), Common Terminology Criteria for Adverse Events (CTCAE) v 5.0. These criteria have been reviewed by the study investigators and have been determined appropriate for this study population.

14.3 Definitions

14.3.1 Adverse events

An AE is any occurrence or worsening of an undesirable or unintended sign, symptom, laboratory finding, or disease that is experienced during participation in the trial. An AE can therefore be any unfavorable and unintended sign (including an abnormal laboratory finding), symptom, or disease temporarily associated with the use of a medicinal (investigational) Study Agent(s) or a study procedure, whether or not related to the medicinal (investigational) Study Agent(s) or study procedure. Any medical condition that is present at the time that the subject is screened will be considered as baseline and not recorded as an AE. However, if the condition deteriorates or changes in severity at any time during the study it will be recorded and reported as an AE.

14.3.2 Suspected adverse reaction and adverse reaction

Suspected adverse reaction (SAR) means any AE for which there is a reasonable possibility that the drug caused the AE. For the purposes of safety reporting, 'reasonable possibility' means there is evidence to suggest a causal relationship between the drug and the AE. A SAR implies a lesser degree of certainty about causality than adverse reaction (AR), which means any adverse event caused by a drug.

An AR means any AE caused by a drug. ARs are a subset of all SARs for which there are reasons to conclude that the drug caused the event.

14.3.3 Adverse events associated with study procedures

The following clinical situations and laboratory parameters will be considered to be outside of the normal range of findings and will be recorded as AEs. These situations do not limit the PI from reporting any other events, associated or not with these procedures, from being recorded and reported as AEs.

Blood draws

- Fainting/vasovagal events
- Bruising at puncture site greater than 2 cm in diameter
- Bleeding from puncture site lasting more than 5 minutes
- Swelling at puncture site larger than 2 cm

14.3.4 Adverse events associated with laboratory testing

The following table highlights the laboratory values that are being obtained as part of the study along with the reference range for normal values. While any value outside the reference range will be classified as abnormal, the clinical significance of those abnormal values will be determined based on the criteria set forth in the table. All lab values identified as clinically significant will be marked as an AE. The causality and attribution of the lab value to the study drug, as well as action items with regards to follow-up and management of laboratory values that are listed as clinically significant, will be adjudicated on an individual basis by the study PI.

Laboratory parameter	Reference Range	Reported as clinically significant if
Serum Creatinine	0.50 – 0.99 mg/dl	≥1.5 times baseline
AST	10 – 35 U/L	≥ 105 U/L (3 times ULN)
ALT	6 – 29 U/L	≥ 87 U/L (3 times ULN)
Hemoglobin	11.7 – 15.5 gm/dl	Decrease of ≥2gm/dL from baseline
Total white blood cells	3.8 – 10.8 x 10 ³ /µL	≤ 3 or ≥ 11.5 x 10 ³ /µL
Absolute neutrophils	1500 – 7800 cells/µL	< 1,000 or > 9,500 cells/µL
Absolute lymphocytes	850 – 3900 cells/µL	< 500 or > 4500 cells/µL
Absolute monocytes	200 – 950 cells/µL	< 150 or > 1,500 cells/µL
Absolute eosinophils	15 – 500 cells/µL	< 5 or > 1,000 cells/µL
Absolute basophils	0 – 200 cells/µL	> 500 cells/µL
Platelet count	140 – 400 x 10 ³ /µL	< 120 or > 450 x 10 ³ /µL

Abbreviations: AST = Aspartate aminotransferase, ALT = Alanine aminotransferase, MCH = Mean corpuscular hemoglobin, MCHC = Mean corpuscular hemoglobin concentration, MCV = Mean corpuscular volume, RDW = Red blood cell distribution width.

While the guidance above is meant to cover all laboratory values obtained during the study, we realize that it may not be able to cover all the unique circumstances that can arise during the conduct of a clinical trial. As such, in rare situations, the study PI may change the clinical significance of a lab value outside of the above guidance. We do not anticipate this situation to arise commonly, however, and if deviating from the above range while assigning clinical significance, the reason for this diversion will be clearly outlined in the subject's study binder. Adverse events related to study medication will be tabulated by body system and by severity using the NCI CTCAE v 5.0.

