3.2 Lymphopenia and other poor prognostic biomarkers in COVID-19

A variety of laboratory parameters have emerged as prognostic biomarkers in patients with COVID-19 that can portend an increased propensity to progress towards acute respiratory distress syndrome (ARDS) and death. Key prognostic biomarkers reported thus far include elevated serum levels of ferritin, d-dimer, LDH, and lymphopenia.^{7,8} Lymphopenia has been observed in 60-80% of the hospitalized COVID-19 patients.⁸⁻¹¹ Absolute lymphocyte count is inversely proportional to disease severity in patients with COVID-19 and patients with worse lymphopenia have increased risk of progression to ARDS and death.^{7,8}

3.3 T lymphocytes play a critical role in viral clearance in patients with SARS as well as COVID-19

Lymphopenia was also seen in 50-80% of cases and predicted poor prognosis in patients with severe acute respiratory syndrome (SARS),^{12,13} a similar illness to COVID-19 that also assumed epidemic proportions and was caused by a related coronavirus, SARS-CoV. Analysis of blood and autopsy specimens from SARS patients revealed the presence of viral particles within circulating and tissue resident lymphocytes, thus implicating direct viral damage as the mechanism for the observed lymphopenia.¹⁴ T-lymphocytes have been demonstrated to play a crucial role in viral clearance in SARS,¹⁵ and play a key role in inhibiting the hyper-activation of innate immunity.¹⁶ A recent single cell transcriptome analysis performed on bronchoalveolar lavage fluid specimens obtained from six hospitalized individuals with COVID-19 revealed that

patients with mild disease had a more robust CD8 T cell adaptive immune response compared to patients with severe disease.¹⁷

3.4 Sirolimus is effective against a variety of viral pathogens including influenza as well as related coronaviruses

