4.1 Main Study Objective

The main objective of our study is to determine if treatment with sirolimus can improve clinical outcomes in hospitalized patients with COVID-19.

4.2 Primary Endpoint:

Progression to respiratory failure requiring advanced support measures, either due to inadequate ventilation (non-invasive or invasive mechanical ventilation) or inadequate oxygenation (CPAP* or high flow supplemental oxygen at rates \geq 15 liters/minute), in patients given sirolimus compared to the placebo group.

4.3 Secondary Endpoints:

Key secondary endpoints:

- Escalation in level of care
- Increase in total lymphocyte count
- Normalization of biomarkers (Ferritin, LDH, and d-dimer)
- Survival to hospital discharge
- Drug safety profile (Incidence and type of adverse and serious adverse events)

Other outcomes measures:

- Fever
- Duration of advanced respiratory support
- Duration of hospital stay (in survivors)
- Time from treatment initiation to death (in non-survivors)
- Need for initiation of other off-label rescue therapies such as Anti IL-6 agents, at the discretion of treating clinicians

* CPAP use for known obstructive sleep apnea will not be considered as disease progression.

5. Study Design

We will employ a randomized, double blind, placebo-controlled study design. 30 patients hospitalized with COVID-19 and meeting the inclusion criteria specified below will be randomized to receive sirolimus or placebo in a 2:1 manner. The treatment regimen and duration are provided in Sections 5.5 and 5.6.

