5.2 Inclusion Criteria

Subjects enrolled in the trial must meet **all** of the following criteria.

- Confirmed COVID-19 pneumonia
- Hypoxia as defined by room air oxygen saturation less than 92% or supplemental oxygen requirement
- Presence of at least one additional biomarker that has been shown to predict poor prognosis: a) serum ferritin $\geq 500\text{ug/l}$, b) LDH $\geq 250\text{U/L}$, c) d-dimer $\geq 1\text{ug/L}$, or d) lymphopenia as defined by absolute lymphocyte count $<1,000/\text{uL}$
- Age ≥ 18 years
- Completed informed consent

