The vast majority of the common side effects (e.g. hyperlipidemia, increased risk of malignancies) are of concern with prolonged/long-term use of sirolimus. Since our study duration is limited to 14 days, these measurements may not be of significant concern. Side effects of particular interest given the nature of this study will be incidence of secondary infections and other organ system toxicities (pneumonitis, increased serum creatinine, decreased blood counts). We will carefully monitor for all laboratory abnormalities at baseline and on days 3, 7, and 14. We will also enquire about any possible AEs from the patients at days 1, 3, 7, and 14.

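### Nine of the eleven laboratory AE limits in Section 14.3.4 ignore baseline, which conflicts with the baseline rule in 14.3.1 and leaves the count of laboratory AEs undefined for patients who enter beyond a limit

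*Combined protocol and SAP*

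**What the plan says.** Section 14.3.4 (protocol) gives a reference range and a clinical-significance limit for 11 laboratory tests, and then: "All lab values identified as clinically significant will be marked as an AE". For lymphocytes the limit is "< 500 or > 4500 cells/µL". Creatinine (at least 1.5 times baseline) and hemoglobin (a fall of at least 2 g/dL from baseline) are the only rows with a baseline term. The section lets the principal investigator depart from the table with a documented reason, but presents this as exceptional.

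Section 14.3.1 sets the general rule. A condition "present at the time that the subject is screened will be considered as baseline and not recorded as an AE"; if it worsens during the study, it is recorded.

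Section 5.2 requires "Presence of at least one additional biomarker that has been shown to predict poor prognosis". One of the four options is "lymphopenia as defined by absolute lymphocyte count" below 1,000/µL, with no lower bound. Sections 5.2 and 5.3 set no limit on platelets, white cells, AST or ALT. Section 4.3 lists both the adverse event profile and "Increase in total lymphocyte count" as key secondary endpoints. Section 9.1 names decreased blood counts among the side effects of particular interest.

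**The concern.** Two staff members who follow the protocol faithfully could code the same patient differently. One applies the 14.3.4 table and records a lymphocyte AE in a patient whose count was already below 500/µL and has not fallen. The other applies 14.3.1 and records nothing. The protocol gives no order of precedence, and the two sections do not refer to each other on this point.

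What is at stake is the meaning of the laboratory AE count. AE incidence is a key secondary endpoint, and Section 14.1 sends AE patterns and frequencies to the DSMB at 7, 15, 22 and 30 subjects. With so few patients, a handful of events that only restate baseline disease severity can blur the picture, and so can a real fall that stops just short of a limit.

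**Working it through.** **The plan's own derived figures.** The AST and ALT limits are described as 3 times the upper limit of normal: 3 × 35 = 105 U/L and 3 × 29 = 87 U/L. Both reproduce exactly.

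**Rows with and without a baseline term.** Baseline-referenced: creatinine and hemoglobin, 2 of 11 (18%). Fixed: AST, ALT, total white cells, neutrophils, lymphocytes, monocytes, eosinophils, basophils and platelets, 9 of 11 (82%).

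**The two sections applied to the same illustrative patients.** Change = (later − baseline) / baseline. Lymphocytes are per µL, platelets ×10³/µL.

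| Course | Change | 14.3.4 table | 14.3.1 |
|---|---|---|---|
| Lymphocytes 300 → 480 | +180/300 = +60% | AE | not an AE (present at screening, improving) |
| Lymphocytes 450 → 450 | 0% | AE | not an AE |
| Platelets 119 → 119 | 0% | AE | not an AE |
| Lymphocytes 510 → 499 | −11/510 = −2.2% | AE | worsening, no threshold given |
| Lymphocytes 1,500 → 500 | −1,000/1,500 = −66.7% | not flagged | no threshold given |
| Platelets 390 → 125 | −265/390 = −67.9% | not flagged | no threshold given |
| Platelets 400 → 140 | −260/400 = −65% | not flagged; still inside the reference range | no threshold given |

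The first three rows are the direct conflict. The last three show the opposite gap: the table is silent, and 14.3.1 supplies no numeric criterion for a laboratory fall. Section 14.4.1 does not close the gap, because it leaves significance to the principal investigator and points back to the 14.3.4 criteria.

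**How many patients could be affected.** Section 3.2 says "Lymphopenia has been observed in 60-80% of the hospitalized COVID-19 patients", but that concerns lymphopenia in general. The share below 500/µL is not given, so the following are assumptions only. Expected patients flagged with no change from baseline = 30 × share:

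- 5%: 1.5 (1 sirolimus, 0.5 placebo)
- 10%: 3 (2 and 1)
- 20%: 6 (4 and 2)
- 30%: 9 (6 and 3)

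The expected proportion is the same in both arms, because baseline counts precede treatment and allocation is random.

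**The case against.** The strongest reply is that 14.3.1 is itself the exemption. It is the general AE definition, it covers abnormal laboratory findings, and a sensible reader would apply it first. On that reading only a cross-reference is missing. The principal investigator may also override the table, lymphocytes of 550, platelets of 125 or an ALT of 85 are still classed as abnormal because they lie outside the reference ranges, and any fixed limit leaves cases just short of it. The data are not lost, since Section 8.3 schedules laboratory tests at baseline and on days 3, 7 and 14.

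Much of this stands as a limit on the size of the problem. It does not remove the conflict: 14.3.4 is worded to cover all values meeting its criteria, and an override meant for unusual cases is not a plan for a common feature of the disease.

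A reader might infer more than the documents support:

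- **That lymphopenia as an entry criterion is logged as an AE.** It is one of four alternative biomarkers, and its limit (1,000/µL) is twice the AE limit (500/µL). Patients entering at 500 to 999/µL are not flagged.
- **That large on-treatment falls can never be recorded.** They are not flagged by the table. The investigator may still record them.
- **That an unchanged baseline abnormality would lead to the dose being held under 12.3.2.** That section ends a hold at grade 1 or baseline, a condition that an unchanged value already meets. Section 14.7 also requires an association with giving the study product before an event is rated possibly related.
- **That the AE comparison is biased between arms.** A chance imbalance in a baseline trait at 20:10 is ordinary sampling variation and would arise whatever the table said. Causality is adjudicated for each event, and the aggregate reports are broken down by attribution.

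**Conclusion.** The concern holds as an unreconciled conflict between 14.3.4 and 14.3.1. For patients already beyond one of nine fixed limits at baseline, the protocol gives two answers on whether an unchanged or improving value is an AE. For patients who start well inside a limit, the table alone can pass over falls of about two thirds in tests that Section 9.1 singles out for attention, and capture then depends on discretion.

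The effect is noise in AE counts in both arms, not a directional bias. Its size cannot be stated from the documents; the 1.5 to 9 patients above rest wholly on assumed shares of 5% to 30% entering below 500/µL, and on the table being applied literally. The primary endpoint and its 80% confidence interval are untouched. The change is worth making because AE incidence is a key secondary endpoint and the remedy is cheap.

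**What to change.** 1. In 14.3.4, state that 14.3.1 governs any value already beyond a limit at baseline, so that such a value is an AE only if it worsens. A rise in CTCAE v5.0 grade from baseline is one workable definition, since 14.6.1 already adopts that grading.
2. Apply this to all nine fixed-limit rows, so that they sit alongside the creatinine and hemoglobin rows.
3. Report these tests to the DSMB and in the safety analysis as baseline-to-worst shift tables by arm. The categories already in 14.3.4 would serve (within reference range, abnormal, beyond the limit), with a summary of change from baseline so that falls short of a limit can be seen.

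The cost is protocol wording and one table layout. For AST, ALT, white cells, lymphocytes and platelets no new samples are needed, because 8.3 already schedules them at baseline and on days 3, 7 and 14. Neutrophils, monocytes, eosinophils and basophils appear in 14.3.4 but are not named in 8.3, so their shift tables would use whatever differential counts are available. The small downside is that each flag needs a comparison with baseline.
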